3.1 Primary Outcome

Diagnostic Reasoning Accuracy Score: This will be a composite score (expressed as a percentage) based on a structured rubric that evaluates the following components for each clinical vignette:

1. **Quality of Differential Diagnoses:** (0-3 points)
 - 0: No reasonable differential diagnoses listed.
 - 1: One reasonable differential diagnosis listed.
 - 2: Two reasonable differential diagnoses listed.
 - 3: Three or more reasonable differential diagnoses listed, including the correct diagnosis.
2. **Supporting Findings:** (0-1 points per diagnosis)
 - 0: No relevant supporting findings listed.
 - 1: Some relevant supporting findings listed, but incomplete.
 - 2: Comprehensive list of relevant supporting findings.
3. **Opposing Findings:** (0-1 points per diagnosis)
 - 0: No relevant opposing findings listed.
 - 1: Some relevant opposing findings listed, but incomplete.
 - 2: Comprehensive list of relevant opposing findings.
4. **Top Choice Diagnosis Accuracy:** (0-18 points)
 - 0: Incorrect final diagnosis.
 - 9: Partially correct final diagnosis (e.g., correct category but wrong specific diagnosis).
 - 18: Correct final diagnosis.
5. **Appropriateness of Next Steps:** (0-1 points per step)
 - 0: Inappropriate or unnecessary next steps.
 - 0.5: Partially appropriate next steps (e.g., some necessary tests missing).
 - 1: Appropriate and comprehensive next steps.

The total score for each vignette will be the sum of these components.

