All participants will complete a comprehensive AI-literacy training program covering LLM capabilities, limitations, prompt engineering techniques, and output evaluation strategies before beginning the trial. Responses will be evaluated by blinded reviewers using an expert-developed assessment rubric specifically designed to detect uncritical acceptance of erroneous information. This naturalistic approach will yield insights directly applicable to real clinical workflows, where increasing cognitive demands can progressively impact diagnostic decision quality, while providing evidence on scalable interventions to preserve clinical judgment in AI-augmented diagnostic settings.

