 - **Orange Signal:** Displayed when the ensemble confidence exceeds the established baseline average but remains below 100%. The choice of orange (vs. yellow) is a deliberate nudge to prevent automation bias and maintain clinical scrutiny.
 - **Green Signal:** Displayed when the ensemble reaches a consensus of 100% confidence. Standard caution will apply (e.g., “AI may make mistakes. Always double-check.”) to guard against over-reliance.

Randomization: Participants will be randomly assigned to either the intervention or control arm in a 1:1 ratio using a computer-generated random number sequence.

Blinding: Outcome assessors (those scoring the diagnostic reasoning performance) will be blinded to the participants’ group assignments. Participants will be blinded to the study’s specific hypothesis regarding automation bias but will be informed they are evaluating LLM diagnostic assistance tools.

Measuring change in automation bias: The primary measure of the change in automation bias will be the mean difference in diagnostic reasoning accuracy scores between the treatment and control arms. A positive difference favoring the treatment arm will indicate the reduction in automation bias attributable to the nudge.

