2.4 Clinical Vignettes & LLM Recommendations

Participants will evaluate six clinical vignettes specifically designed to measure automation bias. These vignettes will:

- Be based on modified real cases.
- Represent a range of diagnostic complexity across common medical specialties.
- Avoid overly simplistic or extremely rare conditions.
- Follow a standardized format, including:
 - Chief complaint and history of present illness.
 - Relevant past medical, social, and family history.
 - Physical examination findings.
 - Initial laboratory results.
- Include three clinical vignettes whose LLM recommendations contain deliberately introduced clinical reasoning errors and three with accurate recommendations, presented in randomized order. A panel of three licensed physicians will design these errors to be subtle yet clinically significant and detectable by trained clinicians.

- For every vignette, the LLM's recommendations will be pre-generated and fixed. This ensures all participants see identical recommendations for each vignette, the same error in flawed cases and the same correct reasoning in accurate cases, eliminating variance from real-time model variability.

Vignette Selection and Validation:

- A pool of 10 potential vignettes will be created and reviewed by an independent panel of three experienced medical doctors for:
 - Clinical accuracy and realism.
 - Appropriateness of difficulty level.
 - Clarity and completeness of information.
 - In flawed vignettes: subtlety and clinical significance of the introduced errors (errors should be detectable by competent physicians but not immediately obvious).
- Six vignettes will be selected based on the panel's ratings and feedback, aiming for a balanced representation of medical specialties and diagnostic challenges.
- For intervention arm participants, LLM output will be pre-generated and standardized for each vignette to ensure consistency in the presentation of correct or flawed information.

Vignette Completion:

- Each participant will complete all six vignettes in a single, proctored, approximately 75-minute session.
- The order of vignettes will be randomized for each participant to control for order effects and prevent pattern recognition.

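### The primary rubric has no item for adopting the planted error, so the score detects uncritical acceptance only indirectly, and no planned outcome measures adoption itself

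*Combined protocol and SAP*

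**What the plan says.** Section 1 (Introduction) describes the instrument as an "expert-developed assessment rubric specifically designed to detect uncritical acceptance of erroneous information". Section 2.1, under the measurement of change in automation bias, states how the result will be read: "A positive difference favoring the treatment arm will indicate the reduction in automation bias attributable to the nudge".

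Section 3.1 sets out the rubric. It has five items: quality of the differential, supporting findings, opposing findings, final diagnosis and next steps. The final-diagnosis item has three levels: "0: Incorrect final diagnosis", then 9 points for "Partially correct final diagnosis (e.g., correct category but wrong specific diagnosis", and "18: Correct final diagnosis". The items are added without weights or deductions: "The total score for each vignette will be the sum of these components".

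On the planted errors, Section 2.4 says: "A panel of three licensed physicians will design these errors to be subtle yet clinically significant and detectable by trained clinicians". It calls them clinical reasoning errors. It does not say that they must change the final diagnosis, or in which diagnostic category a planted diagnosis should fall.

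Section 2.5.1 records, for each vignette, whether the LLM recommendation was viewed. The only secondary outcome (Sections 3.2 and 4.3) is accuracy of the final diagnosis.

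**The concern.** The plan credits the rubric with a property that its items do not state. No item, deduction or scoring note asks whether the participant took over the planted error. Viewing is recorded, adoption is not, and neither the primary nor the secondary outcome measures adoption directly.

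This matters because Section 2.1 equates the score difference with the change in automation bias. The two can separate on flawed vignettes. A physician who copies a planted diagnosis that happens to be in the correct category gets partial credit. One who detects the error, rejects it and settles on a wrong diagnosis in another category gets none on that item. At stake is the meaning of the primary result: a nudge that lowers acceptance could show less gain than it produced, none, or in the extreme a loss.

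**Working it through.** **The plan's own figure.** Section 2.3 states at least 80% power for an 8-point difference, with SD 16.2, 25 per arm, 4 cases per participant and ICC 0.05 to 0.15. Take the SD as that of a single vignette score. The effective number per arm is 25 × 4 / (1 + 3 × ICC), which is 86.96, 76.92 and 68.97 at ICC 0.05, 0.10 and 0.15. Power is then 90.3%, 86.5% and 82.6% (normal approximation), or 89.1%, 85.1% and 81.1% (t with 48 df). The stated figure reproduces and is not affected by this point.

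**Vignette maximum (assumed).** The documents do not give it. Items 2 and 3 are headed 0-1 per diagnosis but list a level of 2, and the number of next steps is not stated. With three diagnoses:
- findings at 0-1, one next step: 3 + 3 + 3 + 18 + 1 = 28
- findings at 0-1, three next steps: 3 + 3 + 3 + 18 + 3 = 30
- findings at 0-2, three next steps: 3 + 6 + 6 + 18 + 3 = 36

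**Item 4 when the planted diagnosis is wrong but in the correct category.**

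| Response | Item 4 | Copier minus this response |
|---|---|---|
| Copies the planted diagnosis | 9 | – |
| Rejects it, wrong, another category | 0 | +9 |
| Rejects it, wrong, same category | 9 | 0 |
| Rejects it, correct | 18 | −9 |

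With equal marks on the other items, 9 points are 9/28 = 32.1%, 9/30 = 30.0% or 9/36 = 25.0% of the vignette score. One such vignette moves a participant's six-vignette mean by 30.0/6 = 5.0 or 25.0/6 = 4.2 points, against the planned effect of 8.

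**Hypothetical effect of a fall in acceptance.** Let acceptance fall by d = 0.20 on such a vignette. Of those who now reject, let c be the share who reach the correct diagnosis and o the share who choose another category; the rest choose another wrong diagnosis in the same category. For maximum M, the change in mean item 4 score, as a share of the vignette score, is d × 9 × (c − o) / M.

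| c | o | M = 30 | M = 36 |
|---|---|---|---|
| 1 | 0 | +6.0 points | +5.0 points |
| 0.50 | 0.25 | +1.5 | +1.25 |
| 0.50 | 0.50 | 0 | 0 |
| 0.25 | 0.75 | −3.0 | −2.5 |

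The change is negative only when more rejecters leave the category than reach the right answer. If the planted diagnosis instead lay outside the correct category and scored 0, the first row would be 0.20 × 18/30 = +12.0 (or 18/36, +10.0), and no row could be negative. On a mean over all six vignettes, with three flawed and no change on the others, every figure halves.

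**Item 1.** A correct rejecter may also gain 1 point for listing the correct diagnosis. With o = 1 − c and M = 30, the change becomes 0.20 × (10c − 9(1 − c))/30: +6.7 at c = 1, +0.3 at c = 0.5 and −2.8 at c = 0.25. Break-even moves from c = 0.50 to 9/19 = 0.47.

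**Errors outside the diagnosis.** If an error were confined to one next step, accepting it would cost at most 1 point: 1/30 = 3.3% of the vignette score, or 1/36 = 2.8%.

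**The case against.** The strongest defence is that the primary outcome is what the plan says it is. The primary objective, H1 and Section 3.1 all concern diagnostic reasoning scores, and ranking a same-category answer above a wrong-category one is coherent for an accuracy measure. This stands. The rubric is not faulty as a measure of accuracy; only the sentences in Sections 1 and 2.1 go further than it can support.

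It also stands that the rubric is not blind to acceptance. Where the planted diagnosis counts as incorrect, copying it scores 0 against 18 for the right answer.

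Several stronger readings are tempting, and the documents do not support them:
- A reader might infer that same-category planted diagnoses are likely because the errors must be subtle. In Section 2.4 that word describes how hard the error is to detect, not its category, and the vignettes and answer keys are not in the documents.
- A reader might infer that copying earns half of the vignette marks. It is half of item 4.
- A reader might infer that planted errors could well be worth only one next-step point. Section 2.4 also requires clinical significance, and a reasoning error may affect findings and diagnosis too.
- A reader might infer that a positive result would be spurious. Every case worked here shows a smaller gain, no change or a loss; none shows a false positive.

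A remedy that scored the planted diagnosis 0 regardless of category would be debatable. Viewing is discretionary, so it would penalise participants who reached that diagnosis without opening the advice. It would also give two equally wrong answers different scores.

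**Conclusion.** The point holds in a limited form. The plan claims for the rubric a property that its items do not have, and no planned outcome measures adoption of the planted error. The score detects acceptance indirectly and non-specifically.

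The size is conditional. If a planted diagnosis is in the correct category, copying it outscores a wrong-category rejection by 9 points on item 4 (25 to 32 percentage points of the vignette score for maxima of 36 to 28, with equal marks elsewhere). It ties with a same-category wrong rejection and loses by 9 to a correct one. The scenario changes of −3 to +6 points are illustrations that rest on assumed shares, not forecasts. How often the situation arises cannot be known from the documents.

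The consequence is that a real fall in acceptance could be understated on flawed vignettes or, in the extreme, reversed. It does not follow that rejecting flawed advice generally scores lower than accepting it, or that the primary comparison is invalid as a comparison of diagnostic accuracy.

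**What to change.** Leave the rubric scoring unchanged, and make three changes to the text.

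1. **Section 2.4.** Have the panel name in advance, for each flawed vignette, the erroneous conclusion that marks adoption: the wrong final diagnosis, or the specific wrong step if the error lies elsewhere.
2. **Section 3.2, with a matching entry in 4.3.** Add a binary secondary outcome for each flawed vignette: recommendation viewed and pre-named erroneous conclusion adopted. The existing blinded raters code adoption from the responses already collected, and the view indicator already recorded is joined at analysis. Compare the arms in all randomised participants, not only those who viewed, with a mixed model for binary data.
3. **Sections 1 and 2.1.** Describe the score difference as a difference in diagnostic reasoning accuracy. Base statements about reduced automation bias on the adoption outcome together with the score.

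The cost is protocol wording before the vignettes are finalised and one extra code per flawed vignette. No new participants or data collection are needed. The new outcome rests on 25 × 3 = 75 vignette responses per arm at most, so its precision will be limited. The primary result will carry a less sweeping interpretation than the plan now gives it.

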3.2 Secondary Outcomes

- **Top Choice Diagnosis Accuracy:** We will use the *Final Diagnosis Accuracy* as the secondary outcome variable.

4 Data Analysis Plan

4.1 Descriptive Statistics

- Baseline characteristics will be summarized using means and standard deviations for continuous variables (e.g., years of experience) and frequencies and percentages for categorical variables (e.g., gender, specialty).
- Diagnostic reasoning scores and top choice diagnosis accuracy will be summarized using descriptive statistics by group
- LLM consultation rate: For each vignette, a binary indicator will be recorded (1 = participant viewed LLM recommendations; 0 = did not view). The measure is the mean proportion of vignettes (range 0-1) per participant in which recommendations were accessed.

4.2 Primary Outcome Analysis

- A linear mixed-effects model will be used to compare the mean diagnostic reasoning accuracy score between the intervention and control groups.
- **Model Structure:**
 - **Dependent Variable:** Diagnostic reasoning performance score (percentage).
 - **Fixed Effect:** Treatment group (Intervention vs. Control).
 - **Random Effects:**
 - * Participant ID (to account for within-participant correlation across cases).
 - * Vignette ID (to account for potential variability in case difficulty).
 - **Covariates:**
 - * Years of practice post MBBS, gender, and prior experience with LLMs.
- **Primary Comparison:** The difference in mean diagnostic reasoning scores between the two groups, adjusted for random effects and covariates.
- **Significance Threshold:** A two-sided p-value ≤ 0.05 will be considered statistically significant.

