Mitigating Automation Bias in Physician-LLM Diagnostic Reasoning Using Behavioral Nudges

[name], [name], [name],
[name], [name]

Study Protocol and Statistical Analysis Plan

Document Date: December 26, 2025

1 Introduction

Automation bias presents substantial risks in clinical environments, particularly as artificial intelligence (AI) tools become more integrated into healthcare workflows. This cognitive phenomenon describes the tendency of individuals to favor suggestions from automated decision-making systems, even when those suggestions are incorrect. While Large Language Models (LLMs), such as ChatGPT-5.1, hold promise for reducing diagnostic errors by augmenting clinical reasoning, concerns arise about their potential to amplify cognitive biases. Of particular concern is the propensity of LLMs to *hallucinate*, generating plausible but false information, which, when combined with automation bias, can lead clinicians to accept erroneous recommendations without adequate scrutiny.

The emergence of automation bias in medical contexts reflects a complex interplay of environmental and psychological factors. Time constraints in high-volume clinical settings create pressure to accept AI-generated recommendations without adequate scrutiny. Financial incentives that prioritize efficiency over thoroughness may further discourage the critical evaluation necessary for sound clinical judgment. Cognitive fatigue during extended shifts diminishes physicians' capacity for sustained analytical thinking. These contextual pressures interact with psychological mechanisms including diffusion of responsibility, overconfidence in technological solutions, and cognitive offloading, collectively creating conditions where uncritical acceptance of AI-generated recommendations becomes more likely.

This randomized controlled trial evaluates the effectiveness of a behavioral nudge intervention designed to mitigate automation bias among medical doctors utilizing LLM-generated diagnostic recommendations. The primary objective is to determine whether this intervention improves diagnostic reasoning performance scores when physicians evaluate clinical vignettes that include deliberately flawed LLM recommendations. Secondary objectives include assessing whether physician experience level, gender, and prior LLM experience moderate the intervention's effectiveness.

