1.1 Research Question

Does a behavioral nudge intervention combining baseline ChatGPT accuracy information and case-specific color-coded confidence signals reduce automation bias and improve diagnostic reasoning accuracy among physicians with discretionary access to LLM recommendations?

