1.2 Hypotheses

- **Primary Hypothesis (H1):** Physicians receiving the behavioral nudge intervention (baseline accuracy information and case-specific color-coded confidence signals) will demonstrate significantly higher diagnostic reasoning scores when evaluating clinical vignettes with deliberately flawed LLM recommendations compared to physicians receiving the same LLM recommendations without the nudge.
- **Secondary Hypotheses:**
 - **H2:** Physicians with less clinical experience will exhibit greater baseline automation bias and show larger treatment effects from the nudge intervention compared to more experienced clinicians.
 - **H3:** The intervention will demonstrate greater effectiveness for red-signal (below-baseline) versus orange-signal (above-baseline) recommendations.

2 Methods

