4.6 Exploratory Analyses

- **Differential Impact of Confidence Signals:** We will compare diagnostic scores for vignettes receiving Red Signal (flawed) versus Orange Signal versus Green Signal by group.

- **Chronometric Analysis of System 2 Engagement:** Using timestamps, we will compare time spent on Red Signal versus Orange Signal vignettes within the Treatment group. Longer durations on Red Signal vignettes would indicate deeper System 2 processing.
- **Physician-Case Specialty Match:** Exploratory analysis will test whether automation bias is lower when a vignette matches the physician's specialty, independent of AI accuracy or signal type.

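### H1 concerns vignettes with flawed LLM advice, but the primary model averages over flawed and accurate vignettes, so a positive result cannot by itself show reduced automation bias as Section 2.1 states

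*Combined protocol and SAP*

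**What the plan says.** The target is stated in two ways.

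- **Flawed vignettes.** H1 in Section 1.2, the only hypothesis labelled primary, expects "significantly higher diagnostic reasoning scores when evaluating clinical vignettes with deliberately flawed LLM recommendations". The primary objective in Section 1 asks whether the nudge "improves diagnostic reasoning performance scores when physicians evaluate clinical vignettes that include deliberately flawed LLM recommendations", which could mean the flawed vignettes or the mixed set that contains them.
- **All vignettes.** The research question in Section 1.1 is whether the nudge will "improve diagnostic reasoning accuracy among physicians with discretionary access to LLM recommendations". Section 2.1 states: "The primary measure of the change in automation bias will be the mean difference in diagnostic reasoning accuracy scores" between the arms. Section 4.2 states: "A linear mixed-effects model will be used to compare the mean diagnostic reasoning accuracy score between the intervention and control groups". Its model has treatment group, three participant covariates, and participant and vignette random effects.

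Section 2.4 has each participant complete six vignettes, three with introduced errors and three with accurate advice. Section 3.1 scores every vignette, and Section 4.5 treats the score as running across all six. Section 4.2 does not itself say all six, but it gives no restriction.

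Section 2.1 then fixes the interpretation: "A positive difference favoring the treatment arm will indicate the reduction in automation bias attributable to the nudge". The nearest separate look is H3, "The intervention will demonstrate greater effectiveness for red-signal (below-baseline) versus orange-signal (above-baseline) recommendations", with this exploratory analysis in Section 4.6: "We will compare diagnostic scores for vignettes receiving Red Signal (flawed) versus Orange Signal versus Green Signal by group".

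**The concern.** Section 1 describes automation bias as favouring automated suggestions even when they are wrong. A reduction in that bias should therefore show on the vignettes with wrong advice. The primary coefficient does not isolate those vignettes. A vignette random intercept absorbs case difficulty, but it does not let the treatment effect differ between flawed and accurate cases.

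Two things are at stake. First, if the effect on accurate vignettes is smaller than on flawed ones, or negative because physicians become too sceptical (a risk that the anchoring-cue text in Section 2.1 recognises), the primary result understates the effect that H1 describes. Second, the overall difference does not show which vignettes a gain came from, yet Section 2.1 attaches the automation-bias conclusion to it. If the target stays open, the choice between a pooled and a flawed-only reading could be made after the results are known.

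**Working it through.** **Inputs.** From Section 2.3: 25 per arm, difference 8 points, SD 16.2, ICC 0.05 to 0.15, an average of 4 completed cases, two-sided alpha 0.05. From Section 2.4: three flawed and three accurate vignettes, all six to be completed.

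**Assumptions.** 16.2 is the SD of a single-vignette score. Data are balanced. SD and ICC carry over to each vignette type. Covariates are ignored. The documents give no effect by vignette type, so every split below is an illustration.

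**Formulas.** With m vignettes per participant, SE = sqrt(2 × 16.2² × (1 + (m − 1) × ICC) / (m × 25)). Power comes from the noncentral t with 48 df and noncentrality (effect / SE). With equal numbers of each type, pooled effect = (flawed effect + accurate effect) / 2. Paired results are for ICC 0.05 and 0.15.

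**Step 1: the plan's own figure.** With m = 4, SE = sqrt(524.88 × 1.15 / 100) = 2.457 and sqrt(524.88 × 1.45 / 100) = 2.759. Power for 8 points is 89.1% and 81.1%. The plan's figure of at least 80% reproduces, if the 8 points are the average over the cases analysed.

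**Step 2: pooled model, six completed.** SE = sqrt(524.88 × 1.25 / 150) = 2.091 and sqrt(524.88 × 1.75 / 150) = 2.475.

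| Flawed / accurate effect | Pooled effect | Power, ICC 0.05 | Power, ICC 0.15 |
|---|---|---|---|
| 8 / 8 | 8 | 96% | 89% |
| 8 / 4 | 6 | 80% | 66% |
| 8 / 0 or 0 / 8 | 4 | 47% | 35% |
| 8 / −4 | 2 | 16% | 12% |
| 8 / −8 | 0 | 5% | 5% |

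The splits 8/0 and 0/8 give the same pooled effect and the same chance of significance. The primary result therefore cannot distinguish a gain on flawed advice from one on accurate advice.

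**Step 3: pooled model, four completed, two of each type.** For 8/0 the pooled effect is again 4 points. With the Step 1 standard errors, power is 36% and 30%.

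**Step 4: contrast on one vignette type.**

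| Vignettes of that type completed | SE | Power for 8 points | 95% CI half-width (2.011 × SE) | Per arm for 80% power |
|---|---|---|---|---|
| 3 | 2.775 / 3.016 | 81% / 74% | 5.6 / 6.1 | 25 / 29 |
| 2 (about what 4 of 6 leaves) | 3.320 / 3.475 | 66% / 62% | 6.7 / 7.0 | 35 / 38 |

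**Step 5: form of the separate-contrast model.** In null simulations (40,000 trials per cell, balanced data, no covariates), a treatment × error-status model with intercepts only rejected on the flawed contrast in 5.1% of trials when participants did not differ by vignette type. When such differences were assumed to make up 10% to 20% of variance, it rejected in 6.0% to 7.4%. A participant-by-error-status random effect kept the rate at 4.7% to 5.1%. Participants' flawed-vignette means gave 4.9% to 5.1%.

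**The case against.** Most of the plan points one way. The research question, the Section 2.1 measure, the per-vignette outcome and the Section 4.2 model all describe an overall comparison, and the primary objective can be read to fit. An overall target is sensible, because physicians in practice do not know which advice is wrong, and a pooled score counts blanket distrust of good advice against the nudge. The model is fully specified and, with no effect on any vignette, its test keeps 5%. All of this stands. What is left is H1 and the Section 2.1 conclusion.

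H3 and the colour comparison do offer a separate look, and Section 4.6 labels red as flawed. This helps only in part: the comparison is exploratory, and colour is set by ensemble confidence rather than by whether an error was introduced. Section 1 also says that the rubric is designed to detect uncritical acceptance of wrong information, but the rubric in Section 3.1 lists no such item.

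A reader might infer more than the documents support:

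- *That the primary test is invalid or inflates false positives.* It does neither.
- *That the trial is likely to report a gain on accurate vignettes as reduced bias.* The 0/8 split is only assumed. H3 points to larger effects on red signals, so dilution is the likelier direction.
- *That a flawed-only analysis is always better.* With 8 points on flawed vignettes and six completed, the pooled test is the more powerful once the accurate-vignette effect exceeds about 4.1 (ICC 0.05) to 5.1 points (ICC 0.15). A flawed-vignette gain can also come from blanket distrust or from not opening the panel. At 8/−8 a flawed-only rule would claim benefit in 81% to 74% of trials although average performance is unchanged.

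**Conclusion.** The point holds as a mismatch between H1, the primary analysis and the interpretation rule. The Section 4.2 coefficient is the average of the flawed and accurate effects and answers H1 only if these are equal. The Section 2.1 sentence is wrong as written, because a positive overall difference does not show that the gain arose on flawed advice.

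The size depends on effects that the documents do not give. If 8 points fall on one type and none on the other, pooled power is 47% to 35% with six vignettes completed and 36% to 30% with four. If the effect is 8 points on both types, nothing is lost. These figures rest on the Section 2.3 SD and ICC applying to each type and on balanced completion.

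This should be corrected before analysis. It does not invalidate the primary test.

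**What to change.** 1. **Prespecify two contrasts.** Before analysis, define the treatment contrast on the three flawed and on the three accurate vignettes, each with a 95% CI. Use a treatment × error-status model with participant and vignette intercepts and a participant-by-error-status random effect, or participants' means by vignette type.
2. **Reword the Section 2.1 rule.** Claim reduced automation bias only if the flawed-vignette contrast is positive and significant at two-sided 0.05. Always report beside it the accurate-vignette contrast with its CI and the consultation rate by arm and error status. State that losses on accurate vignettes smaller than about 6 points (about 7 if only 4 of 6 cases are completed) cannot be excluded.
3. **Make H1 and 4.2 agree.** The simplest route keeps the pooled model as primary, rewords the primary objective and H1 to overall performance over good and bad advice, and names the flawed-vignette contrast as first key secondary, tested only if the primary is significant. If the flawed-vignette contrast becomes primary instead, Section 2.3 must restate power for 8 points as about 81% to 74% with all three flawed vignettes completed, and about 66% to 62% if about two remain, assuming SD and ICC carry over.
4. **Complete Section 2.3.** State to which vignettes the 8 points apply, and reconcile the average of 4 completed cases with the six required in Section 2.4.

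**Cost.** The changes are to wording and analysis code. No new data are needed, because viewing is already recorded per vignette (Section 2.5.1). The pooled-primary route loses no power for the primary test, but it changes the stated hypothesis, and the gate means that the automation-bias claim can be made no more often than the pooled test succeeds (at most 47% to 35% at 8/0 with six completed). The flawed-primary route lowers power from 96%–89% to 81%–74% if effects are equal and all six are completed. Keeping 80% then needs 25 to 29 per arm, or 35 to 38 if about two flawed vignettes remain.
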